## **Study Sample**

This trial will not enroll individual participants. Randomization and assessment of study outcomes will occur at the municipal level, and all study outcomes will be assessed at this same level. However, during the study period, all persons who reside in Rhode Island or who experience a qualifying event—defined as a fatal or non-fatal overdose captured by the state’s multicomponent overdose surveillance system—may contribute data to either the PROVIDENT model or the study outcomes.

Based on 2016 data, we expect to observe approximately 1,800 events of fatal or non-fatal overdoses per year (see Table S1 below), which will be analyzed to evaluate the effects of the community-level intervention. Since all 39 cities/towns in Rhode Island will participate in the intervention trial, and due to the population-based nature of the fatal and non-fatal overdose surveillance system, every Rhode Island city and town may be eligible for inclusion in this study.

## **Inclusion/Exclusion Criteria**

There are no exclusion criteria related to this study. The demographic breakdown of the participants representing these outcome events will most likely be similar to that of the available underlying epidemiology of the overdose epidemic in Rhode Island from 2014-2016 data, with approximately 72% male and 80% white.

## **Target population distribution (e.g., women, minorities, etc.)**

[figure not shown]
The target population for this project will be all persons residing in the State of Rhode Island. We anticipate the actual enrollment distribution for qualifying data events will be similar to the underlying epidemiological trends for overdose observed in the state. Currently, fatal and nonfatal overdose events affect all cities and towns across Rhode Island (see Table S1). We expect the demographic breakdown of the participants representing the overdose-related events will be similar to that of the available underlying epidemiology of the overdose epidemic in Rhode Island from 2014-2016 data, with approximately 72% male and 80% white.

## **Power Calculation and Sample Size**

To ensure adequate power, we will consider as the primary endpoint both fatal and non-fatal overdoses occurring at the municipal level. These events will be defined as described in the Primary and Secondary

Outcomes Measures above. These data are captured in the Rhode Island Office of the State Medical Examiner's drug overdose death records database and the Rhode Island Emergency Medical Services Information System. To estimate the power to detect significant differences between overdose rates in treatment and control cities/towns, we examined 2016 municipal-level overdose data. We used a stratified randomization scheme to conduct power simulations. Power was calculated for relative reductions in combined fatal/nonfatal overdose rates ranging from 15 to 30 percent. We used data from 2016 to set the underlying statewide overdose rate. We simulated randomization of each city to treatment versus control, estimated the expected number of events for each city based on population size and treatment assignment, and then used standard calculations for two-sample comparisons of Poisson rates. Due to the finite sample of municipalities with widely varying population sizes, the person-time of exposure in the control and treatment groups will vary depending on how cities are randomized. We therefore calculated power for several simulated randomizations, with 10 randomly selected instances shown (Figure S1). As shown, we will have at least 95% power to detect a >25% reduction in the treatment arm compared to cities/towns assigned to the control arm. These estimates are conservative: we assumed only one year of post-intervention follow-up time, whereas we anticipate two years based on the project timeline.

**Figure S1:** Power curves for the PROVIDENT trial from simulated randomizations (ten randomly selected instances are shown).

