## **B. Analysis and Data Management**

### **Analysis:**

The analysis plan will be finalized and uploaded to the Open Science Framework (osf.io) before the start of the data analysis in accordance with the pre-specified analysis plan. We will employ standard methods for community intervention trials. The intervention effect will be quantified as a composite fatal and non-fatal overdose incidence rate ratio. We will have at least 5 years of data (from 2016 to 2020) to serve as the pre-intervention period. The trial formally began in November, 2021. We will exclude a six-month 'ramp up' period in all analyses to allow time for the targeted interventions to be deployed. We will have approximately two years of post-intervention data from May 15, 2022, to August 15, 2024.

We will use generalized linear mixed-effect modeling with Poisson or negative binomial link functions to estimate incidence rate ratios comparing overdose rates in treatment cities/towns to control cities/towns. Each municipality will have its own random intercept and slope to account for pre-intervention differences and time trends. Municipal population size will be incorporated as an offset, and 95% confidence intervals will be calculated using standard bootstrapping techniques to account for possible overdispersion of the data and the relatively small number of geographic units per arm. Although we will use stratified randomization to reduce pre-intervention differences in the treatment and control groups, potential biases from the imbalance can be corrected by including other covariates in the model. For example, measures of municipal-level racial/ethnic composition (e.g., percentage Hispanic/ Latino) will be included as covariates, given some evidence of imbalance in these variables between the two arms. Next, we will construct time-lagged regression models to consider the delayed impact of the interventions by staggering outcomes by zero to 6 months.

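### The stated 95% power is a Poisson-only figure with no between-town variance; for a 39-town trial it holds only if residual town-by-period variation is small, which the SAP does not show

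*SAP*

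**What the plan says.** SAP section A, Power Calculation and Sample Size, describes simulated stratified randomisations of the municipalities. The rate input is common to all towns: "We used data from 2016 to set the underlying statewide overdose rate". Each simulation then "estimated the expected number of events for each city based on population size and treatment assignment", and the authors "used standard calculations for two-sample comparisons of Poisson rates". Effects examined were "relative reductions in combined fatal/nonfatal overdose rates ranging from 15 to 30 percent". The only difference between simulated allocations that the section names is person-time per arm. It gives no between-town coefficient of variation, intracluster correlation or design effect.

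The conclusion is that "we will have at least 95% power to detect a >25% reduction in the treatment arm", followed by "These estimates are conservative: we assumed only one year of post-intervention follow-up time", with two years anticipated.

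SAP section B, Analysis, plans a Poisson or negative binomial mixed model. "Each municipality will have its own random intercept and slope to account for pre-intervention differences and time trends". It uses at least five pre-intervention years (2016 to 2020) and a post-intervention window of 15 May 2022 to 15 August 2024, which is 2.25 years. Bootstrap intervals are chosen because of possible overdispersion and the small number of units per arm.

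**The concern.** The power method and the analysis rest on different models. The power method treats the trial as two Poisson counts with a common rate, so towns differ only in size. The analysis expects towns to differ in level and trend. When towns are randomised, any town-specific change between the baseline and follow-up periods adds to the variance of the treatment effect. A calculation without that term gives a best case.

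What is at stake is how the planning claim is read. A reader of a null result could take it as strong evidence against a 25% reduction because the plan claims at least 95% power, when the design may have had less. The estimate, test and interval in section B are not affected.

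**Working it through.** **Inputs.** Table S1 has 39 towns in four strata: Urban-High 6, Urban-Low 4, Non-Urban-High 15, Non-Urban-Low 14. Its rows sum to 1,416 + 323 = 1,739 events in a population of 1,052,567, or 165.2 per 100,000. The printed Total row gives 1,461 + 336 = 1,797, and section A says "we expect to observe approximately 1,800 events of fatal or non-fatal overdoses per year"; the difference does not affect the conclusion. Alpha is not stated for the power calculation; two-sided 0.05 is assumed.

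**1. The plan's own figure.** With equal person-time and one year, the control arm expects 1,739/2 = 869.5 events and the treatment arm 0.75 × 869.5 = 652.1.

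- SE of the log rate ratio = √(1/869.5 + 1/652.1) = 0.0518.
- |ln 0.75| = 0.2877, and 0.2877/0.0518 = 5.55.
- Power = Φ(5.55 − 1.96) = 0.9998.

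Over 4,000 stratified allocations the minimum was 0.9992. The stated floor is met on the plan's own method, so there is no arithmetic error.

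**2. Does Table S1 fit a Poisson model within strata?** With E = stratum rate × town population, X² = Σ(O − E)²/E:

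| Stratum | X² | df | X²/df |
|---|---|---|---|
| Urban-High | 56.0 | 5 | 11.2 |
| Non-Urban-High | 51.0 | 14 | 3.6 |
| Non-Urban-Low | 13.2 | 13 | 1.0 |
| Urban-Low | 2.5 | 3 | 0.8 |
| All | 122.7 | 35 | 3.5 (p about 1e-11) |

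The excess lies in the two High strata. Providence has 541 of 1,739 events (31%); without it the Urban-High ratio falls to 1.5. A negative binomial fit with strata gives overdispersion 0.048 (SE 0.021). That is a CV of √0.048 ≈ 0.22, with a range of roughly 0.08 to 0.30.

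**3. Power with a town-level term.** For town i, the variance of its log pre-to-post rate change is

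v_i = 1/μ_post,i + 1/μ_pre,i + τ²

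Here μ is the expected count (Table S1 stratum rate × population × years, times 0.75 after intervention in treated towns), with 5 baseline years. τ is the residual town-by-period SD of the log rate. Weighting by 1/v_i, the SE of the treatment effect is √(1/ΣT w + 1/ΣC w), where T and C are the treated and control towns. Power comes from a noncentral t with noncentrality 0.2877/SE, averaged over stratified allocations. The documents do not give τ, so it is an assumed range.

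| τ | SE, 1 year | Power, 1 year | SE, 2.25 years | Power, 2.25 years |
|---|---|---|---|---|
| 0.10 | 0.077 | 95% | 0.063 | 99% |
| 0.15 | 0.091 | 86-87% | 0.077 | 95% |
| 0.20 | 0.105 | 75-76% | 0.091 | 86-87% |
| 0.22 | 0.110 | 71-72% | 0.097 | 81-82% |

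The one-point ranges show how far repeat calculations differ. Power is 95% at τ of about 0.10 (one year) or 0.15 (2.25 years), and 80% at about 0.18 or 0.23. If the plan's single statewide rate replaces the stratum rates, the 95% thresholds rise to about 0.13 and 0.18.

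For a 15% reduction, the low end of the plan's range, the pooled Poisson method gives about 85-90% at one year. The formula above gives about 72% (τ = 0.10) to 38% (τ = 0.22) at 2.25 years.

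**4. Why more follow-up is not a general safeguard.** Take Providence as a control town. At the Urban-High rate of 238.3 per 100,000 it expects 424 events a year.

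- One year: 1/424 + 1/2,121 = 0.0028. Adding τ² = 0.04 gives 0.0428, a weight of 23.
- 2.25 years: 1/954 + 1/2,121 = 0.0015. Adding 0.04 gives 0.0415, a weight of 24.

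Extra follow-up helps the small towns, where Poisson noise dominates. It barely changes the contribution of the largest town.

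**The case against.** The strongest reply is that the planned model has five baseline years and town intercepts, so stable differences between towns drop out. That stands. The 2016 spread in Table S1 is cross-sectional and only a proxy for τ. Part of it comes from Providence's level, which a baseline would absorb if stable. Table S1 also does not name the source of its non-fatal counts, while the SAP endpoint uses EMS runs. If τ is about 0.10 or less (one year) or 0.15 or less (2.25 years), at least 95% power survives.

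A reader might infer that the trial lacks 95% power, or that true power could be as low as 40%. The documents support neither. The first needs a value of τ that they do not give. The second comes from pooling towns in proportion to their events, which is not the planned analysis. A reader might also infer that the final analysis ignores clustering; section B addresses it with random effects and bootstrap intervals. Nor do the documents say that the DSMB relies on the 95%.

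It is also fair that *conservative* refers to follow-up alone, and longer follow-up does raise power. But the word is applied to the whole estimate, and the omitted variance works in the other direction.

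The reply does not show that τ is small. The SAP gives no value and itself plans for town-specific slopes. It also records a town-specific change inside the outcome window: the June 2023 Providence protocol that sent all overdose-related 911 calls to EMS. A 2016-2020 baseline cannot remove that.

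**Conclusion.** The concern holds in a conditional form. The 95% is correct for a two-sample Poisson comparison and is not shown for the 39-town design. Over an assumed residual SD of 0.10 to 0.22, power for a 25% reduction runs from about 95% down to 71% at one year, and from about 99% down to 81% at the planned 2.25 years. *Conservative* is unsupported.

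This is a mismatch between the power method and the planned analysis. The figures assume two-sided 0.05, Table S1 stratum rates, inverse-variance weighting, a five-year baseline and one residual SD common to all towns, with no separate random-slope variance. The upper value of 0.22 is borrowed from 2016 cross-sectional data and is imprecise.

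**What to change.** Re-run the power simulation under the section B mixed model, with the five-year baseline and the 2.25-year window. Estimate the town-by-period variance from the 2016-2020 municipal data on the EMS-based endpoint, and show results over a range around it, with and without Providence. Replace the 95% statement with the resulting power at 15%, 20%, 25% and 30% reductions and the reduction detectable at 80% power. State alpha and sidedness, and delete *conservative*. If the Poisson figure is kept for the record, label it as assuming no between-town variation.

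The cost is about a day of simulation and a change of SAP wording. The number of towns, the endpoint and the analysis model stay as they are. The stated power may become less favourable. Section B says the analysis plan is finalised before data analysis starts, so the change fits there.

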## Expected enrollment distribution for cities/towns in Rhode Island (Table S1)

**Table S1:** The target population for this grant will be secondary data events from overdose surveillance records in the State of Rhode Island, randomized at the level of the city/town (2016).

City/Town	Population	Non-Fatal ODs	All fatal ODs	Annual OD Rate (per 100,000)	Urbanicity	Strata
Barrington	16310	9	1	61.31	Non-Urban	Non-Urban-Low
Bristol	22954	15	3	78.42	Non-Urban	Non-Urban-Low
Burrillville	15955	6	1	43.87	Non-Urban	Non-Urban-Low
Central Falls	19376	26	5	159.99	Urban	Urban-Low
Charlestown	7827	12	2	178.87	Non-Urban	Non-Urban-High
Coventry	35014	35	6	117.10	Non-Urban	Non-Urban-High
Cranston	80387	141	16	195.31	Urban	Urban-High
Cumberland	33506	8	10	53.72	Non-Urban	Non-Urban-Low
East Greenwich	13146	7	1	60.86	Non-Urban	Non-Urban-Low
East Providence	47037	51	8	125.43	Urban	Urban-Low
Exeter	6425	7	0	108.95	Non-Urban	Non-Urban-High
Foster	4606	2	1	65.13	Non-Urban	Non-Urban-Low
Glocester	9746	0	2	20.52	Non-Urban	Non-Urban-Low
Hopkinton	8188	17	2	232.05	Non-Urban	Non-Urban-High
Jamestown	5405	1	0	18.50	Non-Urban	Non-Urban-Low
Johnston	28769	42	14	194.65	Non-Urban	Non-Urban-High
Lincoln	21105	17	1	85.29	Non-Urban	Non-Urban-High
Little Compton	3492	1	1	57.27	Non-Urban	Non-Urban-Low
Middletown	16150	10	3	80.50	Non-Urban	Non-Urban-High
Narragansett	15868	11	3	88.23	Non-Urban	Non-Urban-High
New Shoreham	1051	0	2	190.30	Non-Urban	Non-Urban-High
Newport	24672	29	3	129.70	Urban	Urban-Low
North Kingstown	26486	15	7	83.06	Non-Urban	Non-Urban-High
North Providence	32078	39	13	162.10	Urban	Urban-Low
North Smithfield	11967	2	1	25.07	Non-Urban	Non-Urban-Low
Pawtucket	71148	129	29	222.07	Urban	Urban-High
Portsmouth	17389	12	7	109.26	Non-Urban	Non-Urban-High
Providence	178042	449	92	303.86	Urban	Urban-High
Richmond	7708	4	2	77.84	Non-Urban	Non-Urban-Low
Scituate	10329	4	5	87.13	Non-Urban	Non-Urban-High
Smithfield	21430	3	4	32.66	Non-Urban	Non-Urban-Low
South Kingstown	30639	17	2	62.01	Non-Urban	Non-Urban-Low
Tiverton	15780	3	2	31.69	Non-Urban	Non-Urban-Low
Warren	10611	13	2	141.36	Non-Urban	Non-Urban-High
Warwick	82672	132	25	189.91	Urban	Urban-High
West Greenwich	6135	4	1	81.50	Non-Urban	Non-Urban-High
West Warwick	29191	57	11	232.95	Urban	Urban-High
Westerly	22787	46	6	228.20	Non-Urban	Non-Urban-High
Woonsocket	41186	40	29	167.53	Urban	Urban-High
Total	1052567	1,461	336			

## **B. Analysis and Data Management**

### **Analysis:**

The analysis plan will be finalized and uploaded to the Open Science Framework (osf.io) before the start of the data analysis in accordance with the pre-specified analysis plan. We will employ standard methods for community intervention trials. The intervention effect will be quantified as a composite fatal and non-fatal overdose incidence rate ratio. We will have at least 5 years of data (from 2016 to 2020) to serve as the pre-intervention period. The trial formally began in November, 2021. We will exclude a six-month 'ramp up' period in all analyses to allow time for the targeted interventions to be deployed. We will have approximately two years of post-intervention data from May 15, 2022, to August 15, 2024.

We will use generalized linear mixed-effect modeling with Poisson or negative binomial link functions to estimate incidence rate ratios comparing overdose rates in treatment cities/towns to control cities/towns. Each municipality will have its own random intercept and slope to account for pre-intervention differences and time trends. Municipal population size will be incorporated as an offset, and 95% confidence intervals will be calculated using standard bootstrapping techniques to account for possible overdispersion of the data and the relatively small number of geographic units per arm. Although we will use stratified randomization to reduce pre-intervention differences in the treatment and control groups, potential biases from the imbalance can be corrected by including other covariates in the model. For example, measures of municipal-level racial/ethnic composition (e.g., percentage Hispanic/ Latino) will be included as covariates, given some evidence of imbalance in these variables between the two arms. Next, we will construct time-lagged regression models to consider the delayed impact of the interventions by staggering outcomes by zero to 6 months.

To account for Providence's significant contribution to nonfatal overdose events between 2016 and 2024, we will conduct several detailed analyses to assess the impact of the Providence Police Department protocol change (effective June 2023), which directed all overdose-related 911 calls in Providence to EMS. First, we will assess trends in EMS runs for suspected nonfatal opioid overdoses in Providence compared to other municipalities before and after the policy change. We will estimate the time-dependent effects of the protocol change on EMS runs for suspected nonfatal opioid overdose. To evaluate its impact on the trial's primary outcome, we will conduct sensitivity analyses by excluding Providence in one arm and a comparable municipality in the other.

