##### Primary and Secondary Outcome Measures

We will evaluate, at the city/town level, whether prioritized intervention deployment to neighborhoods at high risk of future overdose reduces population-level overdose morbidity and mortality. The primary outcome of the trial will be the cumulative incidence of fatal and non-fatal overdose at the city/town level during the study period. While the PROVIDENT model only forecasts future overdose deaths, we will include a composite measure of municipal-level fatal and non-fatal overdose events as the primary end-point in the trial to ensure adequate power. We will compare fatal and non-fatal overdose rates in the treatment and control municipalities, allowing for a 6-month ramp-up period to allow time for the targeted interventions to be implemented.

Fatal overdoses will be defined as drug-related deaths deemed unintentional by the state medical examiner. Specifically, we will include all deaths that: (1) occur in a Rhode Island municipality; (2) the final manner of death was deemed an accident; and (3) a drug is listed on the death certificate as the primary cause of death or a significant contributing factor. The state-wide nature of Rhode Island's centralized medical examiner system means that all accidental deaths are investigated in a similar and consistent manner (including robust toxicological analyses, death scene investigation, and autopsy by a medical professional); all deaths are certified by the chief medical examiner, resulting in a highly reliable reporting system.

Non-fatal overdoses will be defined as emergency medical services (EMS) runs for suspected non-fatal opioid overdoses identified and classified using the Rhode Island Department of Health-modified Council of State and Territorial Epidemiologists (CSTE) case definition. These data are captured in the Rhode Island Emergency Medical Services Information System (RI-EMSIS) and validated by the Rhode Island Department of Health (RIDOH). The 2022 CSTE guidance identifies suspected nonfatal opioid overdoses when an EMS run meets any of 4 criteria: (1) the provider's primary impression or provider's secondary impression is opioid overdose-related, OR (2) the primary symptom or other associated symptoms is opioid overdose-related, OR (3) medication administered is naloxone and response to medication administered is improved, OR (4) the

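### The SAP does not define a treatment-by-period contrast or name strata or baseline rate as covariates, and readings its text allows give power from roughly 30% to about 80% or more

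*SAP*

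**What the plan says.** The SAP's Analysis section is the fullest statement of the primary model. Mixed models with a Poisson or negative binomial specification are used "to estimate incidence rate ratios comparing overdose rates in treatment cities/towns to control cities/towns". Baseline is handled this way: "Each municipality will have its own random intercept and slope to account for pre-intervention differences and time trends". Population is an offset, and confidence intervals are bootstrapped. The section adds that randomisation is stratified and that "potential biases from the imbalance can be corrected by including other covariates in the model"; the only example given is racial/ethnic composition.

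On data, the section says "We will have at least 5 years of data (from 2016 to 2020) to serve as the pre-intervention period", and describes "approximately two years of post-intervention data from May 15, 2022, to August 15, 2024". It does not say how the two periods are combined. The Primary and Secondary Outcome Measures section describes the same arm comparison after ramp-up: "We will compare fatal and non-fatal overdose rates in the treatment and control municipalities".

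The Power Calculation section "used standard calculations for two-sample comparisons of Poisson rates" and concludes that "we will have at least 95% power to detect a >25% reduction in the treatment arm", assuming one year of follow-up.

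**The concern.** A random intercept or slope describes how towns vary around a common mean. It is assumed independent of arm. If the treatment term is a fixed arm label, nothing in that structure subtracts a baseline difference between the arms. The five pre-intervention years help only if the model holds a contrast that uses them: an arm-by-period term, a treatment indicator that switches on after launch, or the pre-period rate as a covariate. None of these is written.

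Town rates in Table S1 run from 18.50 to 303.86 per 100,000. With 39 towns, a comparison that leaves this spread in the error term is much less precise than the power section implies. The choice also decides what the reported rate ratio means.

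**Working it through.** **1. The plan's own power figure.** The Table S1 rows sum to 1,416 non-fatal and 323 fatal events: 1,739 in 1,052,567 people, or 165.2 per 100,000. The printed totals, 1,461 and 336, give 170.7; the difference does not affect what follows. With an even split, one year and a 25% reduction:

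- expected events: 869.5 control, 869.5 × 0.75 = 652.1 treatment
- SE of the log ratio: √(1/869.5 + 1/652.1) = 0.052
- |ln 0.75| / 0.052 = 0.288 / 0.052 ≈ 5.5; power Φ(5.5 − 1.96) > 99.9%

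Over stratified randomisations of Table S1 the minimum is 99.9%. The stated floor of 95% is reproduced, but by a formula with no between-town variance. Two-sided 5% is assumed here and below, because the SAP gives no alpha.

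**2. Between-town spread.** A Poisson mixed model fitted to Table S1 gives a log-rate SD of 0.58 overall and 0.22 within the four strata (6, 4, 15 and 14 towns).

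**3. Post-period data, arm term, no strata.** Between-town variance alone gives √(0.58² × 2/19.5) = 0.186. Poisson variation over 27 months brings this to about 0.19–0.20, or 0.22 if town trends vary with an SD of 0.10 per year.

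- SE 0.19: 0.288/0.19 = 1.51; Φ(1.51 − 1.96) = 0.33, or 0.31 from a non-central t on 37 df
- SE 0.22: Φ(1.31 − 1.96) = 0.26

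Stratified allocation itself limits the imbalance. The spread of this type of estimate over allocations is about 0.11 on the log scale, so with no effect it lies within about exp(±1.96 × 0.11) = 0.81 to 1.24. The model's SE is therefore too wide. In simulated trials (60–100 per scenario) this analysis rejected in only 10–22% at a true 0.75.

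**4. The same data with strata as covariates.** The SE is 0.087 if town trends do not vary, and 0.136 at a trend SD of 0.10.

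- Φ(0.288/0.087 − 1.96) = 0.91
- Φ(0.288/0.136 − 1.96) = 0.56

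The upper end is optimistic. In Table S1 the high and low strata do not overlap in 2016 rate: urban-low ends at 162.10 and urban-high starts at 167.53; non-urban-low ends at 78.42 and non-urban-high starts at 80.50. The strata appear to be set from those rates, so they should explain 2022–2024 rates less well.

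**5. Both periods with an arm-by-post term, keeping the planned random intercept and slope.** The estimate is 0.75.

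| Trend SD per year (assumed) | Post-only with strata: power | Arm-by-post: power |
|---|---|---|
| 0 | 91% | 100% |
| 0.03 | 87% | 98% |
| 0.06 | 75% | 87% |
| 0.10 | 56% | 78% |

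These figures also assume an extra town-year log SD of 0.10. Simulated fits with a term for that variation gave about 92% and 88% at trend SDs of 0.03 and 0.06, with 3–5% rejection under no effect. A treatment indicator set to 0 in all pre-period rows gave nearly the same results. Plain Poisson without such a term rejected in 23–25% under no effect.

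**6. Both periods pooled under a time-fixed arm term.** With 60 pre and 27 post months at a constant underlying rate and no random slope: (60 + 27 × 0.75)/87 = 0.92. That is ln 0.92 / ln 0.75 ≈ 28% of the log effect. Simulated fits with random slopes, time centred at 2020, gave 0.89–0.92.

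**The case against.** The SAP gives no model equation, and a sensible analyst may code treatment as 0 before launch. With that coding the planned random intercept and slope do use the baseline years, and the estimate is 0.75. The text leans that way: it names a pre-intervention period and speaks of an intervention effect, and Protocol section 12.2 labels the outcome a change. The SAP also does not rely on random effects alone, since it cites stratified randomisation and covariates. It promises a finalised plan before analysis, which may settle the coding. All of this stands, and it makes the point one of specification.

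Four stronger readings are tempting and are not supported:

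- *The random effects cannot adjust for baseline.* That holds for a time-fixed arm term, not for a time-varying one.
- *Allocation luck badly biases the result.* The crude arm rate ratio does range over 0.67–1.49 across stratified allocations with no effect. The SAP does not plan a crude ratio, and its mixed model gives Providence (541 of 1,739 events) much less weight. The matching range is about 0.81–1.24.
- *The effect will be diluted to 0.92.* This needs towns coded as treated from 2016. The text does not exclude it, but it is the less likely reading, and it cannot hold together with the post-only one, which is not diluted.
- *The town slope absorbs the effect and must be replaced.* With an arm-by-post term and the slope kept, simulated estimates were 0.74–0.76.

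**Conclusion.** The point holds as a gap in specification with a material consequence. The written contrast is arm against arm, the stated means of handling baseline differences does not serve that contrast if arm is fixed over time, and neither strata nor baseline rate is named as a covariate. Power for a 25% reduction is roughly 30% on post data without strata, 56–91% with strata, and about 78% or more with an arm-by-post term.

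The between-town SDs come from one year, 2016. Trend and extra-variation SDs are assumptions. Racial/ethnic covariates might recover some precision in the unadjusted case, but the documents give no data to size this. The SEs are model-based, whereas the SAP plans a bootstrap whose resampling unit it does not state. The documents do not show that the planned estimate is biased, or that the trial is bound to be underpowered.

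**What to change.** In the finalised plan, state that the primary rate ratio is the exponentiated arm-by-post-period coefficient or, near-equivalently, that of a treatment indicator set to 0 in every pre-intervention row. Fit it to the 2016–2020 and 15 May 2022 to 15 August 2024 counts, with calendar-time effects, the randomisation strata as covariates, a person-time offset and the planned town random effects. State how overdispersion is handled. If only post-period data are used, adjust for the strata and for each town's pre-period rate. Recompute power for the chosen model with between-town variance included.

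This takes a few sentences and one power run. It needs no new data and no change to the random slope. It should be settled before the plan is posted to the Open Science Framework.
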